Rhode Island Diastolic Dysfunction – Heart Failure (RIDD-HF)

NCT02353312

9/22/2016

Study Title: Rhode Island Diastolic Dysfunction – Heart Failure (RIDD-HF)

Primary Investigator: [name]

Version Date: 12/12/14; 2/10/15, 5/10/16, 9/22/16

Rationale:

Congestive heart failure carries a significant epidemiologic and economic burden in today's healthcare system and is associated with increased morbidity and mortality in those affected. There are approximately 5 million people in the United States with heart failure, and of those, nearly half have heart failure with preserved ejection fraction (HFpEF)¹. HFpEF, also referred to as diastolic heart failure, is a clinical syndrome characterized by prolonged relaxation of the myocardium resulting in symptoms including dyspnea, edema, fatigue, and decreased exercise tolerance, which are clinically indistinguishable from the presentation of heart failure with reduced ejection fraction (HFrEF). The underlying mechanisms in diastolic dysfunction are not clearly elucidated, making targeted therapy a challenge². There are currently no FDA approved treatments for this syndrome, and multiple clinical trials have demonstrated that standard treatments for systolic heart failure are ineffective in treating diastolic dysfunction ³⁻⁶. The current standard of care for HFpEF includes blood pressure control with beta-blockers, ACE inhibitors, and angiotensin receptor blockers (ARBs) in accordance with current clinical practice guidelines, as well as the use of diuretics for management of symptoms due to volume overload.

One of the proposed underlying mechanisms of diastolic dysfunction is via the reduction of nitric oxide (NO), an endothelium-derived vasodilator that regulates blood pressure and regional blood flow⁷. In 2010, Silberman et al. examined the effect of cardiac oxidation on nitric oxide and found that depletion of tetrahydrobiopterin (BH4), an essential cofactor in the production of nitric oxide, causes uncoupling of nitric oxide synthase, impaired relaxation of cardiac myocytes, and leads to subsequent diastolic dysfunction. The authors further went on to demonstrate that treatment with BH4 can improve diastolic dysfunction in a hypertensive mouse model as well as in isolated cardiac myocytes and may play a role in the treatment of HFpEF⁸.

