At this visit, the study will be explained in detail to the patient, and inclusion and exclusion criteria will be reviewed by the study team members. If the patient meets the eligibility criteria and is willing to participate, written informed consent will be obtained. Following the completion of informed consent, the subjects will undergo a limited history and physical exam.

Blood will be drawn for measurement of basic chemistry panel, complete blood count, fasting lipid panel, liver function tests, and the following biomarkers: BNP, glutathionylated myosin binding protein C, adiponectin, aldosterone, endothelin-1, NT-procollagen III, uric acid, and derivatives of reactive oxygen metabolites (DROM). These blood tests have been examined in various studies as markers of the presence of heart failure, ability to respond to treatment of heart failure, or early diagnosis of heart failure¹¹⁻¹⁵.

Subjects will then receive a weight-based test dose of 10mg/kg (rounded to the nearest hundred) of the study medication (Kuvan®(sapropterin dihydrochloride),) and the subject will be observed with blood pressure and oxygen levels being recorded every thirty minutes for one hour. If at any point during this time period, the subject develops hypotension (Systolic Blood Pressure [SBP] <90 or a drop in SBP >20mmHg with associated dizziness or syncope), hypoxemia (decrease in oxygen saturation to <90% on room air), or any evidence of an allergic reaction (pruritus, rash, hives, Heart Rate>100, abdominal cramping, nausea, emesis, or angioedema), the subject will not participate further in the study. Subjects experiencing any of the above symptoms will receive appropriate monitoring and clinical care, potentially including hospital admission, supplemental oxygen, IV fluids, until they are stabilized.

The patients who tolerate the test dose will complete the Kansas City Cardiomyopathy Questionnaire and receive a baseline echocardiogram.

Informed Consent Procedure:

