Kuvan®(sapropterin dihydrochloride) is the synthetic form of the naturally occurring essential cofactor BH4 that is FDA approved for the treatment of phenylketonuria at the recommended dose of 10-20mg/kg daily. This study **does not require an IND waiver** as set forth by the **FDA guidelines listed below:**

"The clinical investigation of a drug product that is lawfully marketed in the United States is exempt from the requirements of this part [investigational new drug application] if all the following apply:

- (i) The investigation is not intended to be reported to FDA as a well-controlled study in support of a new indication for use nor intended to be used to support any other significant change in the labeling for the drug;*
- (ii) If the drug that is undergoing investigation is lawfully marketed as a prescription drug product, the investigation is not intended to support a significant change in the advertising for the product;*
- (iii) The investigation does not involve a route of administration or dosage level or use in a patient population or other factor that significantly increases the risks (or decreases the acceptability of the risks) associated with the use of the drug product;*
- (iv) The investigation is conducted in compliance with the requirements for institutional review set forth in part 56 and with the requirements for informed consent set forth in part 50; and*
- (v) The investigation is conducted in compliance with the requirements of 312.7."*

The study drug will be provided by BioMarin (Committee decision letter attached below – Appendix A)

Compliance will be assessed by monitoring pill counts with the assistance of the research pharmacist.

Follow up visits:

Patients will attend routine follow up visits as outlined below. These visits will occur within one week of the proposed outlined schedule. At all study visits, a brief history and physical exam will be performed and subjects will be evaluated for medication compliance, adverse reactions, and exacerbation history. In addition, interim ED visits and hospitalizations will be assessed for. Any exacerbations of heart failure, defined as worsening in dyspnea (including orthopnea or paroxysmal nocturnal dyspnea), Jugular Venous Pressure elevation, significant weight gain (>3 lbs in 3 days) or lower extremity edema will be recorded.

Summary of follow up visits is as follows:

6 week visit (thirty minutes) – Brief history and physical exam

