Patients will be contacted via phone at weeks 1, 3, 9, 16, and 22. During these phone calls, patients will be asked the questions outlined in Table 2. Additionally, the patients will be seen in person in a research clinic during weeks 6, 12, 13, 19, and 25. At these clinic visits, patients will be asked the questions listed in Table 3. The research team will meet every 4 weeks to review study progress and adverse events. Additionally, all data will be reviewed to assure that no physiological findings warrant immediate intervention. If so, the participant will be contacted and advised of the findings and offered assistance with appropriate referrals. Data from the echocardiogram, laboratory tests and cardiopulmonary exercise testing procedures will be reviewed by the investigators and any unusual or adverse findings will be communicated to the participant's primary care physician. Adverse events will be defined as per the BioMarin Standard Language for Adverse Event Report (below, and attached in Appendix D) and reported to the IRB in accordance with the rules regulating each severity class (expected vs. unexpected, serious vs. other, related vs. unrelated).

BioMarin Standard Language for Adverse Event Reporting: IST Program, Kuvan

According to the ICH definition, an adverse event (AE) is any untoward medical occurrence in a patient or clinical investigation subject administered a pharmaceutical product, and that does not necessarily have a causal relationship with this treatment. An AE can therefore be any unfavorable and unintended sign (including an abnormal laboratory finding), symptom, or disease temporally associated with the use of a medicinal (investigational) product, whether or not considered related to the investigational product.

This definition includes intercurrent illnesses or injuries that represent an exacerbation (increase in frequency, severity, or specificity) of pre-existing conditions. Whenever possible, it is preferable to record a diagnosis as the AE term rather than a series of terms relating to a diagnosis.

Adverse event information will be collected in an ongoing fashion through patient reporting AEs to their physician or health care provider. Seriousness and relatedness will be assessed by the treating physician, with appropriate reporting.

A designated primary contact person based at the treatment center will be responsible for the collection and reporting of AEs for patients participating in the program.

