All serious adverse events (SAEs) and pregnancy reports whether or not considered drug-related should be reported to BioMarin Pharmacovigilance within 24 hours of receipt by the investigator/sponsor by using the FDA 3500A (MedWatch Form). Clinicians should not wait to collect additional information that fully documents the event before notifying BioMarin's Pharmacovigilance Department of an SAE or pregnancy. BioMarin may be required to report certain SAEs to regulatory authorities within 7 calendar days of being notified about the event; therefore it is important that clinicians submit additional information requested by BioMarin Pharmacovigilance as soon as it becomes available.

Reporting of SAEs to the IRB will be done in compliance with the standard operating procedures and policies of the IRB and with applicable regulatory requirements.

Follow up visits:

Patients will undergo routine follow up visits as outlined in Table 1 to assess compliance with medication use, changes in symptoms, development of adverse reactions and further data collection.

Monitoring for Adverse Events (AEs)

At the baseline clinic visit and each follow-up contact, subjects are to notify study staff if they experience any change in their medical condition or medications, or have urgent care visits, emergency room visits, or hospitalizations. Study staff will also monitor for interim emergency room visits or hospitalizations through patient notification system in CPRS to ensure timely reporting. The investigator will contact participants if any reported adverse event suggests clinical deterioration warranting immediate medical attention. During the study, if a subject experiences medical problems or hospitalization, the study medication will be continued unless complicated by symptomatic hypotension. If discontinued, it would be resumed once baseline clinical status is confirmed, assuming the event was not felt to be related to the study medication itself.

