Table 2 - Telephone Monitoring:

Side Effects – fevers, nausea, vomiting, diarrhea, rhinorrhea?
Compliance and barriers to compliance?
Have there been changes in previous medication regimen?
Weight loss/gain?
Is dyspnea improved, worse, or unchanged?
Is there any subjective change in exercise tolerance?
Have there been any doctor's visits or hospitalizations?

Table 3 - Brief History and Physical:

Vital Signs:
Temperature
HR
Respiratory Rate
Oxygen Saturation
Weight
Limited Exam:
HEENT: JVD
CVS: S3
Chest: Crackles
Abd: HJR, Pulsatile Liver
Ext: Edema?
Side Effects – fever, nausea, vomiting, diarrhea, rhinorrhea?
Compliance and barriers to compliance?
Have there been changes in previous medication regimen?
Weight loss/gain?
Is dyspnea improved, worse, or unchanged?
Is there any subjective change in exercise tolerance?
Have there been any doctor's visits or hospitalizations?

References

- 4) Hernandez AF, et al. Clinical effectiveness of beta-blockers in heart failure: findings from the OPTIMIZE-HF (Organized Program to Initiate Life-saving Treatment in Hospitalized Patients with Heart Failure) Registry. *J Am Coll Cardiol*. 2009; 53:184-192
- 6) Pitt B, et al. Spironolactone for Heart Failure with Preserved Ejection Fraction. *N Engl J Med* 2014; 370:1383-1392
- 8) Silberman GA, et al. Uncoupled Cardiac Nitric Oxide Synthase Mediates Diastolic Dysfunction. *Circulation* 2010; 121: 519-528.

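### Table 3 omits blood pressure from the clinic-visit vital signs, so no on-treatment reading is scheduled in the available text, although symptomatic hypotension is the criterion for interrupting drug during an intercurrent event

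*Combined protocol and SAP*

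**What the plan says.** The table headed "Table 3 - Brief History and Physical" lists the vital signs as "Temperature HR Respiratory Rate Oxygen Saturation Weight", followed by a limited examination and a set of questions. The Data and safety monitoring section links the table to the visits at weeks 6, 12, 13, 19 and 25: "At these clinic visits, patients will be asked the questions listed in Table 3". The Follow up visits section adds that "At all study visits, a brief history and physical exam will be performed", without naming any further measurement.

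Blood pressure is prescribed in one place. After the 10 mg/kg test dose at the screening visit, "the subject will be observed with blood pressure and oxygen levels being recorded every thirty minutes for one hour". Hypotension is defined numerically there, and only there: systolic pressure below 90, or a fall of more than 20 mmHg with dizziness or syncope. The same paragraph lists a heart rate above 100 among the signs of allergic reaction that end participation.

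Under the baseline visit, Group 1 starts at 10 mg/kg and moves to 20 mg/kg after a telephone contact on day 7 if no adverse effects are noted. Under Monitoring for Adverse Events, when a subject has a medical problem or is admitted, "the study medication will be continued unless complicated by symptomatic hypotension". On restarting: "If discontinued, it would be resumed once baseline clinical status is confirmed", provided the event was not attributed to the drug.

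**The concern.** The protocol names a blood-pressure event as the exception to continuing drug through an intercurrent illness, but its list of visit measurements leaves blood pressure out. The Rationale makes the omission harder to regard as incidental. The treatment is meant to restore production of nitric oxide, described as "an endothelium-derived vasodilator that regulates blood pressure and regional blood flow", in patients whose standard care already includes blood-pressure drugs.

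Two things are at stake. First, the investigator who must decide whether an event is hypotension, whether it is drug-related and whether baseline status has returned would have no scheduled on-treatment reading to refer to. Second, a crossover pilot could compare each subject's blood pressure on and off drug at almost no cost. A site following the written list would not collect the data for that comparison. The primary outcome, peak VO2, is not affected.

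**Working it through.** This is a check of text against text; the protocol gives no figure to reproduce.

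**Step 1. Where is blood pressure scheduled?**

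| Section | Blood pressure prescribed? |
|---|---|
| Screening visit, test dose | Yes: every 30 minutes for 1 hour after 10 mg/kg |
| Baseline visit | No: brief interview and CPET |
| Follow up visits, weeks 6, 12, 13, 19, 25 | Not named; history and physical exam only |
| Table 1 | No blood-pressure or vital-signs row |
| Cardiopulmonary exercise test | Not named; gas exchange and EKG heart rate and rhythm |
| Table 2, telephone calls at weeks 1, 3, 9, 16, 22 | No; prompts do not name dizziness or syncope |
| Table 3 | Not listed |

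Blood pressure is therefore prescribed at 0 of 5 follow-up clinic visits and 0 of 5 telephone contacts.

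**Step 2. How many on-drug examinations does this cover?** Group 1 is on drug at weeks 6 and 12, and Group 2 at weeks 19 and 25. That is 2 on-drug clinic visits per subject, and 2 × 30 = 60 if all subjects complete. Each subject also has 2 visits in the control period, so the design could support a within-subject comparison.

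**Step 3. Which dose do the prescribed readings cover?** They follow one dose of 10 mg/kg. In Group 1 the first period is 12 weeks, or 12 × 7 = 84 days. The first 7 are at 10 mg/kg, leaving 84 − 7 = 77 days at 20 mg/kg with no scheduled reading. The 13 week visit text gives no titration schedule for Group 2, so the day count is not extended to that group.

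**Step 4. Does the measurement list match the triggers?**
- Intercurrent event: the trigger is symptomatic hypotension. The symptoms can be reported, but no on-treatment pressure is scheduled and the numeric definition is confined to the test dose.
- Restarting: the condition is confirmed baseline clinical status. No blood pressure is prescribed at the baseline visit.
- Test dose: a heart rate above 100 is an exit sign, but only blood pressure and oxygen levels are listed for recording. This is a smaller mismatch of the same kind.

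**The case against.** A reader might infer more than the text supports.

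- **Blood pressure is never measured on treatment.** The documents show only that it is not scheduled in the available text. The interruption rule operates during illness or admission, when clinical care would ordinarily produce readings, and staff follow emergency visits and admissions through the record system. The CPET description is not exhaustive, and a physician is present. The protocol also refers its account of data collected to an addendum that is not available, and a table row lost in PDF reading cannot be excluded, though the list shows no gap. So it cannot be said that the pilot would end with no blood-pressure data.
- **Hypotension is the only reason to stop drug.** It is not. The Protection against risk section has a subject who becomes pregnant stop at once. Hypotension is the only stated criterion for interruption during an intercurrent medical event. At the test dose it is one of three exit categories, alongside hypoxemia and allergic reaction.
- **There is no pre-treatment reference.** A criterion based on a fall in systolic pressure implies a pre-dose reading at screening. What is missing is a prescribed reading at the baseline visit.
- **The plan would miss asymptomatic falls that its own rule covers.** The rule concerns symptomatic hypotension, so an asymptomatic fall lies outside it. Symptoms can also reach staff through open-ended reporting at every contact.

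These points limit the claim but do not remove it. Readings from unscheduled care come only from subjects who fall ill, and the protocol does not require their capture. They cannot replace a measurement at every visit on and off drug. If the addendum does list blood pressure, Table 3 still needs to agree with it.

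**Conclusion.** The point stands in limited form. Table 3 omits blood pressure, and nothing else in the available text schedules a reading on treatment. The prescribed readings cover one hour after a single 10 mg/kg dose, while the protocol goes on to 20 mg/kg and relies on a blood-pressure event as its criterion for interrupting drug during an intercurrent problem. The size is up to 60 on-drug examinations without a scheduled reading and, in Group 1, 77 of 84 treatment days at the higher dose. These figures count missing measurements; they do not estimate harm or bias.

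The conclusion assumes that Table 3 is complete as read, that the unavailable addendum does not add blood pressure, and that all 30 subjects complete both periods. It is a safety-data gap worth closing before the study runs. It does not threaten the primary analysis.

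**What to change.** 1. Add blood pressure to the Table 3 vital signs, so that it is recorded at weeks 6, 12, 13, 19 and 25.
2. Add a blood-pressure reading before randomization to the baseline-visit text and to Table 1. This needs its own line, because Table 3 is not applied to that visit and Table 1 has no history-and-physical entry for it.
3. Add heart rate to the recordings during the one-hour test-dose observation, since it is listed there as an exit sign.
4. Reconcile the screening-visit text, the Monitoring for Adverse Events section and Table 3, and check all three against the addendum cited under Data Collected.

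Thresholds, and the rules for stopping or restarting drug, remain with the sponsor and investigator; none is proposed here.

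The cost is one cuff reading at each of 6 visits per subject (5 follow-up plus baseline), or 6 × 30 = 180 readings in all, plus a heart rate at observation times already planned. No visit is added.
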